### **12.2 Sample Size Justification**

In a sub-analysis of the SMART study, baseline sCD14 levels predicted mortality; those who died in the SMART study had a baseline median sCD14 level of 2.47 pg/mL \*10^6

(IQR 2.19 – 2.91), while matched controls had lower levels at 2.23 pg/mL \*10^6 (IQR 2.01 -263). As these differences were statistically significant, we powered our study to exhibit a similar effect size [55].

With a mean of 2.45 pg/mL\*10^6 and a standard deviation of 0.45 pg/mL\*10^6 observed in ART treated subjects in the SMART study (personal communication [name]) and a correlation coefficient of 0.71 (personal communication [name] and [name]), a trial with a total of 40 aviremic patients has a power of 95% (with type I error of 0.05 based on a one-sample paired difference t test) for detecting a 0.20 difference in sCD14 levels between the placebo and rifaximin phases (namely Day 28 and 84) of the study. Due to possible loss to follow-up (10%), 44 patients will be accrued in this study.

### 12.3 Description of the Statistical Methods

This is a double-blind, randomized, crossover placebo-controlled trial of rifaximin use in aviremic HIV-infected subjects.

The primary goal of this study is to compare the sCD14 levels during the rifaximin and placebo phases of the study. Patients who receive steroids or an additional antibiotic during a treatment period will have a pause and then restart the treatment for a complete period (as described on page 29). Thus such patients will have the endpoints measured at the end of each of the two periods and will be included in the primary analysis. A sensitivity analysis will be conducted where such patients are excluded.

Forty-four aviremic subjects will be randomized to either rifaximin followed by placebo or placebo followed by rifaximin (22 per sequence). The following table displays the treatment and control sequence for the study.

Treatment phase 1	Washout	Treatment phase 2
Day 0-28		Day 0-28
22 aviremic subjects receive rifaximin initially	Washout	22 aviremic subjects switch treatment assignments and receive placebo.
22 aviremic subjects receive placebo initially	Washout	22 aviremic subjects switch treatment assignments and receive rifaximin

At the end of this trial, one sample Wilcoxon statistic will be applied to evaluate the primary end points (difference on Days 28 of treatment phase 1 and 2 of the study). The primary endpoints of interest are changes in soluble CD14 levels between the rifaximin and placebo phases of the study. A P value less than 0.05 will be used to claim significance [114]. Statistical tests and confidence intervals will be two sided.

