## **12 STATISTICAL CONSIDERATIONS**

### **12.1 Study Hypotheses**

This is a double-blind, randomized, crossover, placebo-controlled trial of rifaximin use in HIV-infected subjects. In this trial, ART-treated subjects with an undetectable viral load will be enrolled. The primary objective of this study is to compare the changes in sCD14 levels during the rifaximin phase of the study and compare it with the changes in sCD14 during the placebo phase of the study. Specifically the difference in sCD14 levels measured on Days 28 of treatment phase 1 and 2 will be used to assess rifaximin effect. Moreover to deal with a possible secular trend, the difference of differences (the difference of sCD14 levels measured on treatment phase 1 Days 0 and 28 and the difference measured on treatment phase 2 Days 0 and 28) will be examined as well.

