### **Secondary outcomes for statistical considerations**

In the following paragraphs the term paired difference refers to the difference between Days 28 of treatment phase 1 and 2. These differences will be tested using both the Wilcoxon test and the t-test.

The following paired difference will be examined between the placebo and the rifaximin phase of the study

1. Changes in HIV-1-RNA levels
2. Changes in Serum LPS levels
3. Changes in the proportion of CD8+HLADR+, CD8+CD38+, CD8+HLADR+CD38+, CD4+HLADR+, CD4+CD38+, and CD4+HLADR+CD38+ cells.
4. Changes in the soluble markers of inflammation (IL6, TNF $\alpha$ , D-dimer, and hsCRP)

In addition to deal with a possible secular trend, the difference of differences (for example the difference in HIV-1 RNA levels measured on Days 0 and 28 of treatment phase 1 and treatment phase 2) will be examined as well.

The proportions of different types of adverse effects as well as 95% confidence intervals will be reported.

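### The primary one-sample Wilcoxon ignores the randomised sequence although the plan foresees a secular trend, and the sign of the Day 28 difference is not written out by sequence

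*Combined protocol and SAP*

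**What the plan says.** Section 12.3 randomises subjects to rifaximin then placebo, or to "placebo followed by rifaximin (22 per sequence"). The primary analysis reads: "one sample Wilcoxon statistic will be applied to evaluate the primary end points (difference on Days 28 of treatment phase 1 and 2". The next sentence names the contrast: "The primary endpoints of interest are changes in soluble CD14 levels between the rifaximin and placebo phases of the study". Section 12.1 places the comparison by phase: "Specifically the difference in sCD14 levels measured on Days 28 of treatment phase 1 and 2 will be used to assess rifaximin effect". It then adds: "Moreover to deal with a possible secular trend, the difference of differences" between Days 0 and 28 of each phase will be looked at as well.

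Section 12.2 computes power "based on a one-sample paired difference t test", for a difference "between the placebo and rifaximin phases (namely Day 28 and 84) of the study". For the laboratory secondary outcomes, section 12.3 states that "the term paired difference refers to the difference between Days 28 of treatment phase 1 and 2", tested with both the Wilcoxon test and the t-test.

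No section includes a sequence or period term, a stratification or a comparison between sequences, and none gives a subtraction rule for each sequence.

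**The concern.** In a two-period crossover, any shift between phases that affects both treatments alike (P, phase 2 minus phase 1) enters the rifaximin-minus-placebo difference with opposite signs in the two sequences. A one-sample test pools the sequences and treats that separation as noise. The plan randomises the sequences, which is what allows P to be removed, and it expects that a trend may exist. Yet the p-value that decides significance takes no account of it.

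Section 11.1 adds that translocation results are analysed and reported in batches. The documents do not say whether both phases of one subject share a batch. Central testing (section 5.1) works in the other direction.

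At stake are the power of the primary test and, if the sequences end with unequal numbers, a bias in the estimate. The same paired difference is used for the laboratory secondary outcomes. Safety is not affected, since it is reported as proportions with confidence intervals.

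The smaller point is wording. The difference is located by phase number, or by study day in section 12.2. A programmer who took that literally would compute phase 1 versus phase 2, and the drug effect would cancel.

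**Working it through.** **Inputs (section 12.2, units 10^6 pg/mL).** SD 0.45, correlation 0.71, drug effect tau = 0.20, 40 evaluable and 44 accrued, alpha 0.05; two-sided (section 12.3). P is not given; the assumed range is 0 to 0.3. The top value is 1.5 times the drug effect and serves only as an upper bound.

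**1. The plan's figure.** SD of the paired difference = 0.45 × √(2 × (1 − 0.71)) = 0.343. With n = 40 the noncentrality is 0.20/0.343 × √40 = 3.69, and two-sided one-sample t power is 94.9%. The stated 95% is reproduced. With n = 44 it is 96.6%.

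**2. Effect of P.** Rifaximin minus placebo has mean tau − P in the rifaximin-first sequence and tau + P in the other. With equal numbers the mean is tau, so there is no bias, but the variance becomes 0.343² + P². The inflation factor 1 + (P/0.343)² is 1.02, 1.09, 1.34 and 1.77 at P = 0.05, 0.1, 0.2 and 0.3. The 44 completers are then worth 44/1.02 = 43.1, 40.5, 32.8 and 24.9.

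**3. Power.** The t row is closed form. The Wilcoxon and rank-sum rows are simulated (40,000 normal replicates per cell, exact critical values, Monte Carlo error about 0.1 to 0.2 points near 94%).

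| P | 0 | 0.05 | 0.1 | 0.2 | 0.3 |
|---|---|---|---|---|---|
| One-sample t, n = 44 | 96.6 | 96.3 | 95.3 | 90.5 | 81.3 |
| One-sample Wilcoxon, 22/22 | 96.1 | 95.6 | 95.0 | 91.8 | 83.9 |
| Its type I error | 4.8 | 4.9 | 4.3 | 2.4 | 0.8 |
| Rank-sum by sequence, 22/22 | 95.5–95.9 at every P | | | | |
| One-sample Wilcoxon, 20/20 | 94.0 | 93.9 | 92.8 | 88.3 | 79.5 |
| Rank-sum by sequence, 20/20 | 93.6–93.8 at every P | | | | |

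The rank-sum test keeps type I error at about 5% throughout. One-sample t power reaches 90% at P = 0.21 with 44 completers and at P = 0.17 with 40.

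**4. Unequal completers.** Bias = P × (difference in completers)/N.
- 22/18 (four losses in one sequence, not replaced) at P = 0.2: 0.2 × 4/40 = 0.02. One-sample Wilcoxon power is 80% or 94%, depending on which sequence is larger, and type I error is about 3.3%. Rank-sum power is about 93%.
- 24/16 at P = 0.2: 0.2 × 8/40 = 0.04, with type I error of 6.3–6.4%. This split should not arise under the replacement rule and is shown only as a bound.

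**5. The planned difference of differences.** It cancels a step or a linear trend. Its SD is 0.45 × √(4 × (1 − r)), where r is the Day 0 to Day 28 correlation within a phase, which is not given. At assumed r = 0.71, 0.8 and 0.9, t-test power is 76, 90 and 99% with 44, and 72, 87 and 99% with 40.

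**6. Signed literally by phase number (20/20).** With a true effect of 0.20 and P = 0, the one-sample Wilcoxon rejects 2.3% of the time. With no drug effect it rejects 42.6% of the time at P = 0.1 and 94.4% at P = 0.2.

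**7. Study day.** 28 + 28 + 28 = 84 fits a 4-week washout only. With the 6 weeks that section 5.7 allows, 28 + 42 + 28 = 98.

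**The case against.** The planned test is valid. With balanced completers and P up to 0.1 the gain is about one point of power, and at P = 0 the proposed test is marginally weaker. A P of 0.2 equals the whole effect the trial is powered for and is about 8% of the stated mean (0.20/2.45). That is a large shift over a few weeks in subjects suppressed for at least 3 years. The background section cites one study with no measurable sCD14 decline over 48 weeks of therapy and another with only a partial decline after 96 weeks. Sections 5.8 and 10.8 replace non-completers within their allocated sequence, and the Protocol Summary targets 44 completers, so balance is likely. The trend already has a prespecified analysis. The intended contrast is plainly rifaximin versus placebo, and a two-sided test needs only consistent signing.

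Most of this stands, and it limits the point to efficiency. Two parts do not carry through. Accrual over 2 years dilutes a one-off assay step, but a steady drift still moves phase 2 relative to phase 1 in every subject. The difference of differences is supportive only, and its power depends on a correlation the documents do not give.

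**Conclusion.** The concern holds as an inexpensive improvement that should be made. The primary test omits a sequence adjustment that the design already supports, against a threat the plan names. With equal completers the consequence is lost power, not bias or inflated type I error: about one point at P = 0.1, about four at P = 0.2 (91.8% against at least 95.5%) and about twelve at P = 0.3 (83.9% against at least 95.5%), with 22 per sequence. It becomes material only if P approaches the size of the drug effect or the completers are unequal. These figures rest on normal data, the plan's SD and correlation, no carryover, and assumed values of P. The signing point is minor, because the intent is clear and only the rule is missing.

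**What to change.** - **Primary analysis (12.1, 12.3).** Define D for each subject as Day 28 sCD14 in phase 1 minus phase 2. Compare D between the two randomised sequences with a two-sided Wilcoxon rank-sum test at 0.05. Report rifaximin minus placebo as half the Hodges-Lehmann shift (rifaximin-first minus placebo-first) with its 95% CI. The sequences centre D at tau − P and −tau − P, so half their difference is tau. Report completers per sequence.
- **Sample size (12.2).** Name the time points as Day 28 of the rifaximin phase and Day 28 of the placebo phase. Base power on the by-sequence t test: 94.9% with 20 per sequence and 96.6% with 22 (rank-sum about 94% and 96%).
- **Secondary outcomes (12.3).** Use the same by-sequence analysis (rank-sum and two-sample t) for the listed laboratory outcomes. Leave adverse event reporting as it is.
- **Sensitivity analyses.** Keep the one-sample Wilcoxon and the difference of differences, both signed rifaximin minus placebo.

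The cost is an amendment to sections 12.1–12.3 before unblinding. No new subjects, visits or data are needed, and N stays the same. One degree of freedom is spent: at P = 0, rank-sum against one-sample Wilcoxon power is 95.9% against 96.1% (22/22), 93.8% against 94.0% (20/20) and about 93.3% against 93.9% (22/18). Like the present test, it assumes no carryover.

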### **Secondary outcomes for statistical considerations**

In the following paragraphs the term paired difference refers to the difference between Days 28 of treatment phase 1 and 2. These differences will be tested using both the Wilcoxon test and the t-test.

The following paired difference will be examined between the placebo and the rifaximin phase of the study

1. Changes in HIV-1-RNA levels
2. Changes in Serum LPS levels
3. Changes in the proportion of CD8+HLADR+, CD8+CD38+, CD8+HLADR+CD38+, CD4+HLADR+, CD4+CD38+, and CD4+HLADR+CD38+ cells.
4. Changes in the soluble markers of inflammation (IL6, TNF $\alpha$ , D-dimer, and hsCRP)

In addition to deal with a possible secular trend, the difference of differences (for example the difference in HIV-1 RNA levels measured on Days 0 and 28 of treatment phase 1 and treatment phase 2) will be examined as well.

The proportions of different types of adverse effects as well as 95% confidence intervals will be reported.

### **Exploratory Objectives**

Some exploratory objectives to be investigated include:

1. The comparison of changes in gut mucosal biopsies between the placebo and the rifaximin phase of studies will be performed by either paired-t test or paired Wilcoxon test.
2. The comparison of changes in fecal microbiome during the placebo and rifaximin phases of the study will be done by using either paired-t test or paired Wilcoxon test.

## **13 ETHICS/PROTECTION OF HUMAN SUBJECTS**

### **13.1 Informed Consent Process**

Informed consent is a process where information is presented to enable persons to voluntarily decide whether or not to participate as a research subject. It is an on-going

conversation between the human research subject and the researchers about the essential information about the study, which begins before consent is given and continues until the end of the subject's involvement in the research. Discussions of essential information about the research will include the study's purpose, duration, experimental procedures, alternatives, risks, and benefits, and subjects will have the opportunity to ask questions and have them answered. The subjects will sign the informed consent document prior to any procedures being done specifically for the study. The subjects may withdraw consent at any time throughout the course of the trial. A copy of the informed consent document will be given to the subjects for their records. The rights and welfare of the subjects will be protected by emphasizing to them that the quality of their medical care will not be adversely affected if they decline to participate in this study.

### **13.2 Confidentiality**

All records will be kept confidential to the extent provided by federal, state and local law or other applicable law and regulation. The study monitors and other authorized representatives of the Sponsor may inspect all documents and records required to be maintained by the Investigator, including but not limited to, medical records. Records will be kept locked and all computer entry and networking programs will be done with coded numbers only. Clinical information will not be released without written permission of the subject, except as necessary for monitoring by IRB, NIAID, OHRP, or the sponsor's designee.

## **14 DATA MANAGEMENT**

Study data will be collected and maintained on paper Case Report Forms (CRF) at the University of Pittsburgh and WRNMMC. Case Report Forms will be sent to NIH and relevant data placed in CRIMSON. At NIH the Crimson system will be used. Finally, for data analysis all collected data (including Crimson data) will be entered and saved to a password-protected computer spreadsheet (Microsoft ExcelTM) for analysis and review. The study investigators will be responsible for assuring that the data collected is complete, accurate, and recorded in a timely manner. Source documentation (the point of initial recording of a piece of data) should support the data collected on the case report form, and be signed and dated by the person recording and/or reviewing the data. Source documents include all recordings of observations or notations of clinical activities and all reports and records necessary for the evaluation and reconstruction of the clinical trial. Source documents include, but are not limited to, the medical records, laboratory reports, ECG tracings, x-rays, radiologist reports, biopsy reports, ultrasound photographs, progress notes, pharmacy records, and any other similar reports or records of procedures performed during the subject's participation in the protocol. Data for electronic CRFs/ source documents will be collected during study visits, phone calls with subjects and healthcare providers, and abstracted from the medical record.

### **14.1 Types of Data**

Data will include laboratory and clinical data to include signs/symptoms, diagnoses codes, medication use, and clinical history. Data on research tests will also be collected. All data on CRF will be de-identified. A master log of all the subjects enrolled will be

maintained by the principal investigator or their designee. Access to the master log will be restricted. The master log will be kept in a locked cabinet behind locked doors, or in an electronic password protected database.

#### **14.2 Source Documents and Access to Source Data/Documents**

Study data will be collected on source documents and [case report forms (CRF) designed for the study and in an electronic data system (CRIMSON)] at the NIH. Study-specific databases will be developed at WRNNMC and the University of Pittsburgh using Excel. The Principal Investigator at each site is responsible for assuring that the data collected is complete, accurate, and recorded in a timely manner.

## **APPENDIX B: TOXICITY**

The toxicity grading scale for this protocol is the “Table for Grading the Severity of Adult and Pediatric Adverse Events; Version 1.0 - December 2004 (Clarification dated August 2009).”

It can be found at:

[http://rsc.techres.com/Document/safetyandpharmacovigilance/Table\\_for\\_Grading\\_Severity\\_of\\_Adult\\_Pediatric\\_Adverse\\_Events.pdf](http://rsc.techres.com/Document/safetyandpharmacovigilance/Table_for_Grading_Severity_of_Adult_Pediatric_Adverse_Events.pdf)

## **APPENDIX C: COMPENSATION PLAN**

University of Pittsburgh-- Participants will be compensated \$25-\$100 per blood draw depending upon distance traveled and \$200 for each colonoscopy.

NIAID- Participants will be compensated \$40 per blood draw and \$350 for each colonoscopy.

WRNMMC- Participants will be compensated \$40 per blood draw only. There will not be colonoscopy compensation at the WRNMMC site.

## **Appendix D: Reporting Requirements:**

Individual requirements for all three IRBs have been included in the package.

### **NIAID Reporting Requirements**

#### **Expedited Reporting to the NIAID IRB**

Serious and non-serious Unanticipated Problems, deaths, serious deviations, and serious or continuing non-compliance will be reported within 7 calendar days of investigator awareness. Serious Adverse Events that are possibly, probably, or definitely related to the research will be reported to the NIAID IRB within 7 calendar days of investigator's awareness, regardless of expectedness.

#### **Annual Reporting to the NIAID IRB**

The following items will be reported to the NIAID IRB in summary at the time of Continuing Review:

- Serious and non-serious unanticipated problems
- Expected serious adverse events that are possibly, probably, or definitely related to the research
- Serious adverse events that are not related to the research
- All grade 3/4 adverse events.
- Serious and Non-Serious Protocol deviations
- Serious, continuing, and minor non-compliance
- Any trends or events which in the opinion of the investigator should be reported

## Appendix E

As per the USU ID IRB requirements all greater than minimal risk will require an independent medical monitor, the duties of the medical monitor at WRNMMC are detailed below

Duties as the Medical Monitor include:

- 1) Monitoring the conduct of the protocol per the approval plan and ensuring protection of human subjects. This may involve periodic review of medical records of enrolled subjects and the research files being maintained by the PI.
- 2) Reviewing and keeping abreast of protocol reported adverse events and protocol deviations that occur during the research (all adverse events, including deaths and serious or unexpected side effects, are reported to the Medical Monitor via the PI).
- 3) If there is concern about the welfare of enrolled subjects, the Medical Monitor has the authority to stop a research study in progress, remove individual subject from a study, and take whatever steps necessary to protect the safety and well being of research subjects until the IRB can assess the Medical Monitor's report. Notification of such actions must be forwarded to the IRB staff within one (1) working day of receipt of knowledge prompting human subject welfare concerns.
- 4) Medical Monitors will be required to co-sign all adverse event reports, protocol deviation memoranda, Annual Progress Reports, and addendum.
- 5) The Medical Monitor must keep current the required research ethics Human Subjects Training every year.
- 6) If the Medical Monitor is expected to be away for more than 14 days but less than 30, the PI or Medical Monitor must designate an acting Medical Monitor and document such action.
- 7) If a Medical Monitor leaves for greater than 30 days then the PI must be informed to designate a new Medical Monitor and report such change to the IRB via a memorandum for a change of Medical Monitor.
